3.2 Exclusion Criteria

- 1. Prior therapy:
 - a)
 - b) Prior therapy with a VEGF(R) inhibitor alone or in combination with immune checkpoint inhibitor(s).
 - c) Prior therapy with an anti-CTLA-4 antibody
- 2. Participants with active, known, or suspected autoimmune disease. Participants with type I diabetes mellitus, residual hypothyroidism due to autoimmune thyroiditis only requiring hormone replacement, skin disorders (such as vitiligo, psoriasis, or alopecia) not requiring systemic treatment are permitted to enroll.
- 3. Participants with a condition requiring systemic treatment with either corticosteroids (> 10 mg daily prednisone or equivalent) or other immunosuppressive medications within 14 days of study drug administration. Inhaled or topical steroids are permitted in the absence of active autoimmune disease.
- 4. History of allergy or hypersensitivity to any monoclonal antibody
- 5. Previous or concurrent malignancy within 3 years of study entry, with the following exceptions:
 - a) adequately treated basal or squamous cell skin cancer, superficial bladder cancer, prostate intraepithelial neoplasm, carcinoma in-situ of the cervix, or other noninvasive or indolent malignancy; OR
 - b) other solid tumors treated curatively in which the expected rate of recurrence within 5 years is < 5%.

CONFIDENTIAL - Cabozantinib + Nivolimab + Ipililumab Protocol Required Elements

- 6. Impaired cardiovascular function or clinically significant cardiovascular diseases, including any of the following:
 - History of acute coronary syndromes (including myocardial infarction, unstable angina, coronary artery bypass grafting, coronary angioplasty, or stenting) <6 months prior to screening,
 - Symptomatic congestive heart failure (i.e. Grade 2 or higher), history or current evidence of clinically significant cardiac arrhythmia and/or conduction abnormality <6 months prior to screening. Exceptions include asymptomatic/well-controlled atrial fibrillation/flutter or paroxysmal supraventricular tachycardia;
 - Uncontrolled hypertension defined as persistent elevation of systolic blood pressure ≥ 140 mmHg or diastolic blood pressure ≥ 90 mmHg, despite medical therapy
- 7. History of thromboembolic or cerebrovascular events ≤ 6 months prior to the first dose of study treatment. Examples include transient ischemic attacks, cerebrovascular accidents, hemodynamically significant (i.e., massive or sub-massive) deep vein thrombosis or pulmonary emboli.

Note: Individuals with either deep vein thrombosis or pulmonary emboli that does not result in hemodynamic instability are allowed to enroll as long as they are on a stable dose of anticoagulants for at least 4 weeks.

Note: Individuals with thromboembolic events related to indwelling catheters or other procedures may be enrolled.

- 8. Impaired gastrointestinal function or disease that may significantly alter the absorption of cabozantinib (e.g., uncontrolled vomiting or malabsorption syndrome)
- 9. Concurrent neuromuscular disorder that is associated with the potential of elevated CK (e.g., inflammatory myopathies, muscular dystrophy, amyotrophic lateral sclerosis, spinal muscular atrophy)
- 10. Any other condition that would, in the Investigator's judgment, contraindicate an individual's participation in the clinical study due to safety concerns or compliance with clinical study procedures, e.g., infection/inflammation, intestinal obstruction, unable to swallow medication, social/psychological issues, etc.
- 11. Participants who have undergone major surgery (e.g., intracranial, intrathoracic, or intra-abdominal surgery) ≤ 3 weeks prior to starting study drug, minor surgery ≤ 10 days prior to starting study drug or who have not recovered from side effects of such procedure. Subjects must have complete wound healing from major surgery or minor surgery before first dose of study treatment.
- 12. Participants that are pregnant or nursing (lactating)
- 13. Prisoners or individuals who are involuntarily incarcerated
- 14. Medical, psychiatric, cognitive or other conditions that may compromise the participant's ability to understand the patient information, give informed consent, comply with the study protocol or complete the study
- 15. Patients with leptomeningeal involvement by melanoma
- 16. Participants with CNS metastases or leptomeningeal carcinomatosis are not eligible unless:

- 16.1. CNS metastases have been treated and remained stable by radiographic evaluation at least 4 weeks after CNS directed therapy and/or:
- 16.2. There are ≤5 asymptomatic untreated CNS metastases measuring no larger than 10 mm each.
- 16.3. Eligible subjects must be neurologically asymptomatic and without corticosteroid treatment at the time of first dose of study treatment."
- 17. Radiation therapy for bone metastases within 2 weeks, any other radiation therapy within 4 weeks, or systemic treatment with radionuclides within 6 weeks before first dose of study treatment; ongoing clinically relevant complications from prior radiation therapy are not eligible
- 18. Concomitant anticoagulation with coumarin agents (e.g., warfarin), direct thrombin inhibitors (e.g., dabigatran), direct factor Xa inhibitor betrixaban, or platelet inhibitors (e.g., clopidogrel). Allowed anticoagulants are the following:
 - 18.1. Prophylactic use of low-dose aspirin for cardio-protection (per local applicable guidelines) and low-dose low molecular weight heparins (LMWH).
 - 18.2. Therapeutic doses of LMWH or anticoagulation with direct factor Xa inhibitors rivaroxaban, edoxaban, or apixaban in subjects without known brain metastases who are on a stable dose of the anticoagulant for at least 1 week before first dose of study treatment without clinically significant hemorrhagic complications from the anticoagulation regimen or the tumor.
- 19. Administration of a live, attenuated vaccine within 30 days prior to first dose of study treatment
- 20. Evidence of tumor invading the GI tract, active peptic ulcer disease, IBD, diverticulitis, cholecystitis, symptomatic cholangitis or appendicitis, acute pancreatitis, acute obstruction of pancreatic duct or common bile duct, or gastric outlet obstruction
- 21. Abdominal fistula, GI perforation, bowel obstruction or intra-abdominal abscess within 6 months before first dose of study treatment. Complete healing of intra-abdominal abscess must be confirmed before first dose of study treatment
- 22. Clinically significant hematuria, hematemesis, or hemoptysis of >0.5 tsp (2.5ml) of red blood, or other history of significant bleeding within 12 weeks before first dose of study treatment
- 23. Cavitating pulmonary lesion(s) or known endotracheal or endobronchial disease manifestation
- 24. Lesions invading or encasing any major blood vessels.
- 25. History of idiopathic pulmonary fibrosis, organizing pneumonia, drug-induced pneumonitis, idiopathic pneumonitis, or evidence of active pneumonitis on screening chest CT scan.
- 26. Serious non-healing wound/ulcer/bone fracture.
- 27. Moderate to severe hepatic impairment (Child-Pugh B or C).
- 28. Requirement for hemodialysis or peritoneal dialysis.
- 29. History of solid organ or allogenic stem cell transplant.

30. QTcF > 500 msec within 14 days before first dose of study treatment (Note: Could also be listed in Inclusion as \leq 500 msec)

4 STUDY ASSESSMENTS AND PROCEDURES

4.1 Pre-Treatment Period

During the Pre-Treatment Period, subjects are consented and qualified (screened) for the study. Informed consent must be obtained before initiation of any clinical screening procedure that is performed solely for the purpose of determining eligibility for this study. Evaluations performed as part of routine care before informed consent can be considered as screening evaluations if done within the defined screening period, and if permitted by the site's institutional review board (IRB)/ethics committee (EC) policies.

Study eligibility is based on meeting all of the study inclusion criteria and none of the exclusion criteria at screening and on Study Day 1 before study treatment administration. The following assessments will be conducted before subjects receive their first dose of treatment on this protocol:

Screening Procedures	Pre-treatment Period Day -28 through initiation of treatment	Instructions
Informed Consent	X	
Medical History	Х	All medical history relevant to the disease under study including smoking history, alcohol use, AJCC M stage, recreational drug use
Adverse Event Collection	Х	
Concomitant Medications	Х	Complete review of current medications with patient including herbal and dietary supplements, and over the counter (OTC)
Comprehensive Physical Exam	Х	To include basic body systems

Vital Signs	Х	Height, weight, blood pressure, pulse, 02 saturation, respiration
ECOG Performance Status	Х	
Disease Assessment	Х	Contrast enhanced CT of the chest, abdomen, pelvis Or MRI abdomen, w/wo gadolinium contrast including non contrast CT are acceptable for patients with iodine contrast allergies.
Cardiac Assessment	Х	ECHO and ECG
Biopsy	х	Optional biopsy prior to initiation of treatment. In patients who do not consent then archival tissue will be requested.
Laboratory Assessments	Х	See Clinical Safety Laboratory Assessments.
Tumor Markers	Х	LDH
Specimen Collection or Optional Specimen Banking	Х	Serum for banking (4ml lavender top and 4ml red top)

For each subject, the Pre-Treatment Period ends upon receipt of the first dose of study treatment or final determination that the subject is ineligible for the study.

4.1.1 Clinical Safety Laboratory Assessments

Clinical Safety Laboratory Assessments		
Hematology – CBC with Hemoglobin, Hematocrit, Total leukocyte count, including differential and		
Platelet count		
Chamistry		
Chemistry		
Aspartate aminotransferase (AST)	Albumin	
Alanine aminotransferase (ALT)	Sodium	
Total bilirubin Potassium		
Alkaline phosphatase (ALP)	Chloride	

Lactate dehydrogenase (LDH)	Calcium
Creatinine	Phosphorus
Blood Urea Nitrogen (BUN) or serum UREA	СК
Glucose	GGT- screening
Bicarbonate	Magnesium-screening
Total Protein	Troponin - screening
	TSH, and free T4 - screening
	TSH, with reflexive fT4 if TSH is
	abnormal - on treatment
	Lipase and /or amylase
	•

PT/INR/PTT, and drug adherence checks

Serology

Hepatitis B/C, (HBV sAG, HCV antibody or HCV RNA), - screening only

(Testing for HIV-1 and HIV-2 must be performed where mandated by local requirements)

Other Analyses

Serum Pregnancy test (WOCBP only: minimum sensitivity 25 IU/L or equivalent units of HCG).

Follicle stimulating hormone (FSH) screening -only required to confirm menopause in women < age 55)

Urinalysis with UPCR (urine protein creatinine ratio) - screening and at each study visit

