CONFIDENTIAL - Cabozantinib + Nivolimab + Ipililumab Protocol Required Elements

Ipilimumab 1 mg/kg IV			
Day 1 Every 3 weeks	X		
(cycles 1-4)			
Nivolumab 3mg/kg IV			
Day 1 Every 3 weeks	X		
(cycles 1-4)			
Nivolumab 480mg IV		x	
Day 1 every 4 weeks		^	
	Refer to	Refer to	Contrast enhanced CT of the chest,
Disease Assessment	instructions for	instructions	abdomen, pelvis.
Disease Assessificit	interval	for interval	Restaging will occur every 12 weeks (+/-1 week)
Cardiac Assessment	х		ECG/EKG – day 1 of cycles 1-4 only
Specimen Collection or	х	x	Serum for banking (4ml lavender top and
Optional Specimen Banking	^	^	4ml red top)
			(prior to treatment start and on treatment
Biopsy	X		for 10 patients) prestudy and on day 15 for
			consenting patients
Complete Blood Count (CBC)	X*	X	See Clinical Safety Laboratory Assessments.
complete blood count (cbc)	^	^	*Repeat CBC/CMP on D14 of cycles 1-4.
Blood Chemistry	X*	x	See Clinical Safety Laboratory Assessments.
blood Chemistry	^	^	*Repeat CBC/CMP on D14 of cycles 1-4.
			See Clinical Safety Laboratory Assessments.
Thyroid Function Tests	X	X	TSH with reflex to free T4 day 1 of odd
			numbered cycles
Tumor Markers			LDH
Immune Parameters	х	х	Immune parameters assessment. Refer to
			Section 4.4
Study Labs Serum Sample			Please see PK section of the protocol.
Pharmacokinetics (PK)			Section 4.4
Urinalysis UPCR	x	x	UA to evaluate for proteinuria
Pregnancy Test (HCG)	х	х	For WOCBP

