The most frequent AEs experienced by \geq 20% of subjects treated with cabozantinib in descending order of frequency were diarrhea, fatigue, decreased appetite, nausea, palmar-plantar erythodysesthesia syndrome (PPES), vomiting, weight decreased, hypertension, PPES, vomiting, constipation, hypertension, dysgeusia, dysphonia, and asthenia. For a full description of the safety profile of cabozantinib, refer to the cabozantinib Investigator's Brochure.

Subjects may also experience other medically important but less frequent AEs including arterial and venous thrombotic AEs (e.g., deep vein thrombosis [DVT], pulmonary embolism, transient ischemic attack [TIA], and myocardial infarction [MI]), severe hemorrhagic events, proteinuria, wound healing complications, GI perforation, abscesses including intra-abdominal and pelvic abscess, GI and non-GI fistulae formation, osteonecrosis, and RPLS).

Adverse events associated with laboratory abnormalities experienced by ≥ 5% of subjects treated with cabozantinib in descending order of frequency were anemia, AST increased, ALT increased, hypothyroidism, hypokalemia, hypomagnesemia, thrombocytopenia, hypocalcemia, hypophosphatemia, LDH increased, lipase increased, neutropenia, ALP increased, hyponatremia, and leukopenia.

Many AEs can occur early (within the first few weeks) in the course of treatment with cabozantinib, as cabozantinib is expected to reach steady state exposure at approximately 2 weeks following first dose. Events that generally have an early onset include hypocalcemia, hypokalemia, thrombocytopenia, hypertension, PPES, abdominal pain, mucosal inflammation, constipation, diarrhea and vomiting. In addition, earlier onset for events of dehydration was observed in subjects with castrate-resistant prostate cancer (CRPC) when compared with subjects with other tumor types.

Adverse events should be managed with supportive care at the earliest signs of toxicity. Dose reductions and treatment interruptions should be considered. Dose reductions are recommended for events that, if persistent, could become serious or intolerable. Cabozantinib should be discontinued for the following AEs: visceral perforation or fistula formation, severe hemorrhage, serious arterial thromboembolic

events, nephrotic syndrome, hypertensive emergency, persistent uncontrolled hypertension despite optimal medical management, and reversible posterior leukoencephalopathy syndrome (RPLS).

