5.4.1.2.20 Electrolyte Abnormalities

Electrolyte abnormalities, including hypocalcemia, hypokalemia, hypomagnesemia, and hypophosphatemia have been noted in subjects treated with cabozantinib. In some cases these have been Grade 3 or 4 and/or serious. These laboratory values should be evaluated routinely. Deficits should be corrected when an electrolyte abnormality is noted in order to avoid worsening. Correction of electrolyte abnormalities should be accompanied by increased frequency of monitoring.

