13.4 Case Report Forms

For enrolled subjects, all and only data from the procedures and assessments specified in this protocol and required by the CRFs should be entered on the appropriate CRF. Additional procedures and assessments may be performed as part of the Investigator's institution or medical practice standard of care and may not be required for CRF entry.

Clinical data will be recorded on the study-specific electronic case report form (eCRF) in the REDCap clinical data management system (CTMS). For each subject enrolled, the CRF (paper or electronic) must be completed and signed by the PI or authorized delegate from the study staff. This also applies to records for those subjects who fail to complete the study. If a subject stops dosing or terminates from the study, the dates and reasons must be noted.

All paper forms should be typed or filled out using indelible ink and must be legible. Errors should be crossed out but not obliterated, the correction inserted, and the change initialed and dated by the Investigator or his or her authorized delegate.

The Investigator should ensure the accuracy, completeness, legibility, and timeliness of the data in the CRFs and in all required reports.

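### The laboratory table schedules magnesium at screening only, while Section 5.4.1.2.20 names hypomagnesemia as a cabozantinib risk and asks for routine evaluation; the two must be reconciled

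*Combined protocol and SAP*

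**What the plan says.** - **Section 4.1.1, laboratory table.** The magnesium entry is "Magnesium-screening". Calcium, potassium and phosphorus appear in the same chemistry block with no timing tag. Thyroid testing has one line for screening and another ending "abnormal - on treatment". The urine entry reads "Urinalysis with UPCR (urine protein creatinine ratio) - screening and at each study visit".
- **Section 4.2, study assessments.** Blood chemistry is drawn on Day 1 of every cycle, by reference to the Section 4.1.1 table, with the note "Repeat CBC/CMP on D14 of cycles 1-4". Magnesium is not named.
- **Section 4.3, post-treatment visits.** Chemistry at 30 days and at 12 weeks again refers to the Section 4.1.1 table.
- **Section 5.4.1.2.20.** "Electrolyte abnormalities, including hypocalcemia, hypokalemia, hypomagnesemia, and hypophosphatemia have been noted in subjects treated with cabozantinib". The section adds that some of these abnormalities reached Grade 3 or 4 or were serious, and then states "These laboratory values should be evaluated routinely".
- **Section 5.4.1.2.** The laboratory AEs seen in at least 5% of cabozantinib-treated subjects include "hypothyroidism, hypokalemia, hypomagnesemia, thrombocytopenia, hypocalcemia, hypophosphatemia".

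**The concern.** Section 5.4.1.2.20 treats four electrolytes alike. The schedule supports routine evaluation for three of them and not for the fourth, and no section explains the difference. A site working from the schedule would draw no magnesium after screening unless something prompted it.

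Two things are at stake. First, secondary endpoint 5 is the incidence of Grade 3 or higher treatment-related AEs. A laboratory abnormality that is measured only when prompted is ascertained less completely than one on the panel. Second, other rules depend on the value. Under Section 5.4.2.1 a Grade 3 drug-related laboratory abnormality delays nivolumab and ipilimumab, and magnesium is not among the listed exceptions. Under Section 5.4.2.3 a Grade 4 drug-related laboratory abnormality leads to discontinuation, apart from isolated electrolyte abnormalities without sequelae that are corrected within 72 hours of onset. Without scheduled measurements, such an abnormality may go unseen and its onset is hard to date.

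**Working it through.** The plan states no figure on this point, so there is nothing to reproduce. The check is a cross-reading of sections, with counts for scale.

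**1. Does the tag limit timing?** In the same table, thyroid tests have separate screening and on-treatment lines, and UPCR is marked for screening and every visit. Where testing beyond screening is meant for a tagged item, the table says so. Screening-only is therefore the natural reading for magnesium.

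**2. Does another schedule add it?** No. The chemistry rows in Sections 4.2 and 4.3 point back to Section 4.1.1. The Day 14 note refers to a CMP, whose content the documents do not define.

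**3. How many chemistry time points are involved?** Inputs: up to 24 months of treatment (Section 4.2), four 3-week cycles, then 4-week cycles (Section 2).
- 24 × 30.4375 = 730.5 days. Day 1 visits fall at days 0, 21, 42 and 63, then every 28 days from day 84. The last is at 84 + 23 × 28 = day 728. That is 4 + 24 = 28 visits. If 24 months is taken as 104 weeks, (104 − 12)/4 = 23 later cycles, giving 27.
- Adding four Day 14 draws to the 28 gives 32 on-treatment time points. There are two more after treatment.
- This is the maximum. A patient treated for only 5 months (the benchmark median PFS) has 7 Day 1 visits. One treated for 9 months (the benchmark plus the 4-month target improvement) has 11.

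Magnesium is explicitly scheduled at none of these points.

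**4. What else would lead to a magnesium measurement?**
- Clinically indicated extra assessments (Section 4.2), which need a prompt.
- Electrolyte monitoring with vomiting (Section 5.4.1.2.1), which does not name magnesium.
- A check after confirmed QTcF prolongation (Section 5.4.1.2.16), which does name it. Scheduled on-treatment ECGs fall on Day 1 of cycles 1–4 only. The last is at day 63, and 63/730.5 = 8.6% of a full course.
- A site following Section 5.4.1.2.20 over the table.

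**5. How many cases might there be?** Expected cases = n × p; chance of at least one = 1 − (1 − p)^n. The 5% is the documents' floor and is not restricted to Grade 3 or higher. The 10% and 20% rates are assumptions to show a range.

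| n | p | Expected cases | Chance of at least one |
|---|---|---|---|
| 25 | 5% | 1.25 | 72% |
| 25 | 10% | 2.5 | 93% |
| 25 | 20% | 5.0 | 99.6% |
| 41 | 5% | 2.05 | 88% |

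So some hypomagnesemia is likely even in 25 subjects. The table says nothing about how much of it would be Grade 3 or higher, or missed.

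**The case against.** A reader might infer that hypomagnesemia will go undetected and uncounted throughout treatment, and that the Grade 3 or higher rate is therefore biased low. The documents do not support that.

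- **Detection.** The routes in step 4 exist, and Section 5.4.1.2.20 is itself protocol text. Nothing says the table overrides it. The table also prints the word only for serology and not for magnesium. What stands against this is that each route needs a prompt or a site's choice between two conflicting instructions, so ascertainment would be uneven.
- **Counting.** Section 13.4 says "all and only data from the procedures and assessments specified in this protocol and required by the CRFs should be entered", so a magnesium value from routine care might not be entered. But endpoint 5 counts AEs, not laboratory values. Section 7.1.2 covers results from any clinical investigation and asks for an AE report when an abnormal value changes management or is clinically significant, unless it fits the present disease state or pre-study values. Section 7.1.1 also draws AEs from routine and symptom-directed investigations. A measured, relevant abnormality should thus be counted. The CRF clause adds little, and the gap lies in measurement.
- **Size.** One missed case among 25 subjects is 1/25 = 4 percentage points, but only if it is Grade 3 or higher, treatment-related, otherwise undetected and that subject's sole qualifying event. The documents give no probability for that. Their severity statement covers the four electrolyte abnormalities together, and the 5% floor is not grade-specific. Endpoint 5 is descriptive, with no decision threshold.

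These objections limit the consequence. They do not remove the contradiction.

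**Conclusion.** The concern holds as an internal inconsistency with a limited consequence. Section 4.1.1, and Sections 4.2 and 4.3 through it, schedule magnesium at screening only, while Section 5.4.1.2.20 asks for routine evaluation of a group that includes it. Asymptomatic cases may be missed or found inconsistently. Under-ascertainment could only lower endpoint 5, but whether it occurs and by how much cannot be derived from the documents. The nivolumab and ipilimumab rules in Sections 5.4.2.1 and 5.4.2.3 may also be applied unevenly between patients.

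This rests on reading the tag as a limit on timing, which the thyroid and UPCR entries support, and on the chemistry rows adding nothing to the table. The primary endpoint, sample size, alpha and power are unaffected.

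**What to change.** Reconcile Sections 4.1.1, 4.2 and 4.3 with Section 5.4.1.2.20, so that the laboratory table and the routine-evaluation instruction agree. Removing the screening tag would place magnesium in the chemistry panel with the other three named electrolytes and bring the table into line with the protocol's own text. If screening-only is intended, Section 5.4.1.2.20 should say so, and the safety report should state that on-treatment magnesium was not systematically measured. The clinical choice is for the sponsor and the investigator. In either case, state whether the Day 14 CBC/CMP in cycles 1–4 includes magnesium.

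The cost is a table edit and, if the tag is removed, one extra analyte on draws already scheduled. No new visit or procedure is needed.
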